5.1 Imputation rules

All imputation rules will be provided in full details in the PDS and the most updated rules as mentioned in the PDS will be followed.

5.1.1 Study drug

The following rule should be used for the imputation of the dose end date for a given study treatment component:

Scenario 1: If the dose end date is completely missing and there is no EOT page and no death date, the patient is considered as on-going:

The patient should be treated as on-going and the cut-off date should be used as the dose end date.

Scenario 1 should not applicable for final CSR. All patients should have EOT page complete before the Database lock for Final CSR

Scenario 2: If the dose end date is completely or partially missing and the EOT page is available:

Case 1: The dose end date is completely missing, and the EOT completion date is complete, then this latter date should be used.

Case 2: Only Year(yyyy) of the dose end date is available and yyyy < the year of EOT date:

Use Dec31yyyy

Case 3: Only Year(yyyy) of the dose end date is available and yyyy = the year of EOT date:

Use EOT date

Case 4: Both Year(yyyy) and Month (mm) are available for dose end date, and yyyy = the year of EOT date and mm < the month of EOT date:

Use last day of the Month (mm)

All other cases should be considered as a data issue and the statistician should contact the data manager of the study.

After imputation, compare the imputed date with start date of treatment, if the imputed date is ≤ start date of treatment:

Use the treatment start date

Patients with missing start dates are to be considered missing for all study treatment component related calculations and no imputation will be made. If start date is missing then end-date should not be imputed.

5.1.2 AE, ConMeds and safety assessment date imputation

Table 5-1 Imputation of start dates (AE, CM) and assessments (LB, EG, VS)

Missing Element	Rule
day, month, and year	
• No imputation will be done for completely missing dates
day, month	
• If available year = year of study treatment start date then
◦ If stop date contains a full date and stop date is earlier than study treatment start date then set start date = 01JanYYYY
◦ Else set start date = study treatment start date.• If available year > year of study treatment start date then 01JanYYYY• If available year < year of study treatment start date then 01JulYYYY
day	
• If available month and year = month and year of study treatment start date then
◦ If stop date contains a full date and stop date is earlier than study treatment start date then set start date= 01MONYYYY.
◦ Else set start date = study treatment start date.• If available month and year > month and year of study treatment start date then 01MONYYYY• If available month and year < month year of study treatment start date then 15MONYYYY

Table 5-2 Imputation of end dates (AE, CM)

Missing Element	Rule (*=last treatment date plus 30 days not > (death date, cut-off date, withdrawal of consent date))
day, month, and year	
• Completely missing end dates (incl. ongoing events) will be imputed by the end date of the on-treatment period*
day, month	
• If partial end date contains year only, set end date = earliest of 31DecYYYY or end date of the on-treatment period *
day	
• If partial end date contains month and year, set end date = earliest of last day of the month or end date of the on-treatment period*

Any AEs and ConMeds with partial/missing dates will be displayed as such in the data listings.

Any AEs and ConMeds which are continuing as per data cut-off will be shown as 'ongoing' rather than the end date provided.

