7.2.2.5 Laboratory evaluations

Clinical laboratory analyses (hematology, fasting biochemistry (full or partial), fasting lipase, fasting amylase, fasting lipid panel/glucose/c-peptide, HbA1_C, coagulation, pregnancy test and urinalysis) are to be performed by the central laboratory. In case of urgent safety management of hyperglycemia, fasting or random blood glucose assessment may be done locally according to the schedule of assessments and collection plan outlined respectively in Table 7-1 and Table 7-5 for the Core Phase.

Note: as hyperglycemia typically occurs within the first weeks of treatment, blood glucose at Day 8 and Day 15 of Cycle 1 should be performed both locally and centrally for rapid availability for safety evaluation and dose adjustments.

Unscheduled local laboratory assessments may be performed if medically indicated to assess a (potential) adverse event or when the treating physician cannot wait for central laboratory results for decision making (e.g. dose modifications) during the Core Phase. In this particular situation, if possible, the blood sample obtained at the same time point should be submitted to the central laboratory for analysis in parallel with local analysis. During the Extension Phase, all labs will be sent to local laboratory for testing.

The results of the local laboratory during the Core Phase will be recorded in the eCRF if any of the following criteria are met:

- A treatment decision was made based on the local results, or
- Local lab results document an adverse event not reported by the central lab, or
- Local lab results document an adverse event severity is worse than the one reported by the central lab, or
- There are no concomitant central results available

At any time during the study, abnormal laboratory parameters which are clinically relevant and require an action to be taken with study treatment (e.g. require dose modification and/or interruption of study treatment, lead to clinical symptoms or signs, or require therapeutic intervention), whether specifically requested in the protocol or not, will be recorded on the AE eCRF page. Laboratory data will be summarized using the Common Terminology Criteria for Adverse events (CTCAE) version 4.03. Additional analyses are left to the discretion of the investigator.

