- 3. If the patient discontinues fulvestrant on or after Cycle 2 Day 1, then:
 - the last date of exposure to fulvestrant is calculated as (last date of administration of fulvestrant) + (length of time interval - 1) i.e. [last date of fulvestrant administration+ (28-1)].
 - If the patient died or was lost to follow-up within last date of administration of fulvestrant + 27 days, the last date of exposure to fulvestrant is the date of death or the date of last contact, respectively.

Goserelin and Leuprolide

Goserelin and leuprolide were administered (for pre menopausal women and men (cohort B)) on the first day of every cycle (e.g. Cycle 1 Day 1, Cycle 2 Day 1 etc.)

The *last date of exposure to* Goserelina or leuprolide is calculated as follows:

- (last date of administration of Goserelina or leuprolide) + (length of time interval - 1) i.e. [last date of Goserelina or leuprolide administration+ (28-1)].
- If the patient died or was lost to follow-up within last date of administration of Goserelina or leuprolide + 27 days, the last date of exposure to Goserelina or leuprolide is the date of death or the date of last contact, respectively.

Study day

The study day, describes the day of the event or assessment date, relative to the reference start date.

The study day is defined as:

- The date of the event (visit date, onset date of an event, assessment date etc.) – reference start date + 1 if event is on or after the reference start date;
- The date of the event (visit date, onset date of an event, assessment date etc.) – reference start date if event precedes the reference start date.

The reference date for all assessments (safety, efficacy, etc) is the start of any component of the study treatment.

Time unit

A year length is defined as 365.25 days. A month length is 30.4375 days (365.25/12). If duration is reported in months, duration in days will be divided by 30.4375. If duration is reported in years, duration in days will be divided by 365.25.

Baseline

For safety and efficacy evaluations, the last available assessment on or before the date of start of study treatment is defined as “baseline” assessment.

If patients have no value as defined above, the baseline result will be missing.

On-treatment assessment/event and observation periods

For adverse event reporting the overall observation period will be divided into three mutually exclusive segments:

- ***pre-treatment period:***

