from day of patient’s informed consent to the day before first administration of study treatment.
- ***on-treatment period:***
from date of first administration of study treatment to 30 days after date of last actual administration of any study treatment (including start and stop date).
- ***post-treatment period:***
starting at day 31 after last administration of study treatment.

Safety summaries (tables, figures) include only data from the on-treatment period with the exception of baseline data which will also be summarized where appropriate (e.g. change from baseline summaries). In addition, a separate summary for death including on treatment and post treatment deaths will be provided. In particular, summary tables for adverse events (AEs) will summarize only on-treatment events, with a start date during the on-treatment period (***treatment-emergent*** AEs).

However, all safety data (including those from the post-treatment period) will be listed and those collected during the pre-treatment and post-treatment period will be flagged.

Windows for multiple assessments

In order to summarize laboratory parameters, vital sign and other data collected over time (including unscheduled visits), the assessments will be time slotted. The following general rule will be applied in creating the assessment windows: If more than one assessment is done within the same time window, the assessment performed closest to the target date will be used. If 2 assessments within a time window are equidistant from the target date, then the earlier of the 2 assessments will be used. If multiple assessments on the same date then the worst case will be used. Data from all assessments (scheduled and unscheduled), including multiple assessments, will be listed.

Time windows for laboratory assessments

Assessment	Target day of assessment	Time Interval
Baseline		\leq Day 1
Cycle 1 Day 8	8	Day 2 to day 11
Cycle 1 Day 15	15	Day 12 to day 21
Cycle 2 Day 1	29	Day 22 to day 42
Cycle 3 Day 1	57	Day 43 to day 63
Cycle 3 Day 15	71	Day 64 to day 77
Cycle 4 Day 1	85	Day 78 to day 98
Cycle k Day 1 ($k \geq 5$)	$d = (k-1) * 28 + 1$	Day $d-14$ to day $d+13$
End of Treatment		Assessment taken at the end of treatment visit

Last contact date

The last contact date will be derived for patients not known to have died at the analysis cut-off using the last complete date among the following:

Table 2-1 Last contact date data sources

Source data	Conditions
Date of Enrollment	No condition

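### SAP Table 5-1 applies the adverse-event start-date rule to laboratory, ECG and vital-sign dates, so a partially dated post-dose record can become, or tie for, the baseline

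*SAP*

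**What the plan says.** The rule is in SAP Amendment 4, section 5.1.2, to which the extension-phase SAP (2.1) refers for all main analyses. Table 5-1 is titled "Imputation of start dates (AE, CM) and assessments (LB, EG, VS". When only the day is missing, the trigger is "If available month and year = month and year of study treatment start date then". The table first checks for a full stop date before treatment and otherwise applies "Else set start date = study treatment start date". When day and month are both missing, the trigger is "If available year = year of study treatment start date then", with the same two outcomes. Records from a later month are handled differently: "If available month and year > month and year of study treatment start date then 01MONYYYY".

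SAP 2.1.1 says that "the last available assessment on or before the date of start of study treatment is defined as" baseline. No clock time is used and imputed dates are not excluded. The laboratory windows in that section run up to and including Day 1 for baseline, and from Day 2 to Day 11 for C1D8. For several records in a window, it adds: "If multiple assessments on the same date then the worst case will be used".

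SAP 2.8.3 combines central and local laboratory data, then tabulates the worst post-baseline grade and the shift from baseline to the worst on-treatment grade. SAP 2.8.4 reports ECG and vital-sign changes from baseline.

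SAP 5.1 says that full imputation rules are in the PDS and that its latest version prevails. The PDS is not among the documents.

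**The concern.** For an adverse event, moving an uncertain date to Day 1 is cautious, because the event becomes treatment-emergent. For a measurement, the same move can put a value obtained on treatment into the comparator against which later values are judged.

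Elsewhere the SAP guards against this kind of problem. Incomplete tumour-assessment dates have their own rule (5.1.2.1), and completely imputed dates may not define the last contact date (2.1.1). Laboratory, ECG and vital-sign records have no such protection.

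The exposed period is Cycle 1. Protocol 7.2.2.5 notes that hyperglycemia typically appears in the first weeks and says that "blood glucose at Day 8 and Day 15 of Cycle 1 should be performed both locally and centrally for rapid availability for safety evaluation and" for changes of dose. Under that section, a local result enters the eCRF when it drove a treatment decision, documented an adverse event that the central laboratory missed or graded lower, or had no central counterpart. Site-entered local records therefore lean towards clinically important values.

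**Working it through.** No figure in the plan needs reproducing. The check applies the printed rules to the visit schedule.

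**Step 1: which branch applies.** Laboratory, ECG and vital-sign records have no stop date. A partial date in the start month (or the start year, if the month is also missing) therefore always goes to Day 1.

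**Step 2: what is already on Day 1.** Protocol Table 7-1 gives:
- Hematology, chemistry and glucose: screening on Day -14 to -1, nothing at C1D1. Glucose is next taken at C1D8; hematology and partial chemistry at C1D15. An imputed Day 1 result is the latest eligible record and becomes baseline.
- Vital signs: taken at C1D1, C1D8 and C1D15. An imputed record ties with the real Day 1 record.
- ECG: taken pre-dose at C1D1, then only as clinically indicated until end of treatment. An imputed record again ties.

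If the same-date rule in SAP 2.1.1 settles these ties, the more abnormal value wins.

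**Step 3: how often a partially dated sample would move.** Let d be days after first dose. With a start day uniform over a 30.4375-day month, the share still in the start month is (30.4375 − d)/30.4375, or zero when d exceeds the month. As a calendar check, the rule was applied to every start date from 14-Aug-2017 (first screening) to 14-Dec-2020 (enrollment complete), 1,219 dates.

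| Visit | d | Day missing: formula | Day missing: calendar | Day and month missing: calendar |
|---|---|---|---|---|
| C1D8 | 7 | 23.4375/30.4375 = 0.770 | 77.0% | 98.3% |
| C1D15 | 14 | 16.4375/30.4375 = 0.540 | 54.1% | 96.6% |
| C2D1 | 28 | 2.4375/30.4375 = 0.080 | 8.0% | 92.2% |
| C2D15 | 42 | 0 | 0.0% | 87.6% |
| C4D1 | 84 | 0 | 0.0% | 73.8% |
| C7D1 | 168 | 0 | 0.0% | 48.6% |

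Among scheduled blood tests, the C1D8 row concerns glucose only. For hematology and chemistry the first relevant row is C1D15.

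**Step 4: an illustrative record.** First dose is 04-Mar-2019. Screening fasting glucose is 98 mg/dL, taken as normal. The local C1D8 fasting glucose on 11-Mar-2019 is 230 mg/dL (Grade 2 in Protocol Table 6-3, above 160 to 250 mg/dL), and its date is recorded as March 2019. Table 5-1 dates it 04-Mar-2019, so baseline becomes 230 mg/dL.
- With no other C1D8 result, the value leaves the post-baseline data and the shift from Grade 0 to Grade 2 is lost.
- With a fully dated central result of similar size, Grade 2 remains in the worst post-baseline table. The shift table still shows Grade 2 to Grade 2, which is no worsening.

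Inclusion criterion 12 caps fasting glucose at 140 mg/dL, so a Grade 2 fasting baseline would be suspect on its face.

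**Step 5: the opposite direction.** If screening hemoglobin is Grade 1 and a misdated C1D15 value is normal, baseline becomes Grade 0. A later Grade 1 then appears as new worsening.

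**Step 6: patients affected.** The documents give no rate of partial dates. If 0.5% to 2% of patients had one in Cycle 1 (an assumption), a cohort of 112 would have 112 × 0.005 × 0.54 = 0.3 to 112 × 0.02 × 0.77 = 1.7 affected.

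**The case against.** A reader might infer that the rule hides toxicity, and always in that direction. The documents do not support that. Step 5 shows that the error can also exaggerate worsening. Laboratory abnormalities that are clinically significant, need therapy or change study treatment must be reported as adverse events (Protocol 8.1.1, 8.1.2), and the date rule is cautious for those. SAP 2.8.3 lists all laboratory values with grades and lists Grade 3 and 4 values separately. The damage is confined to baseline-relative summaries.

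A reader might also infer that ECG and vital-sign baselines are replaced outright. With a scheduled C1D1 record they are only tied, and the outcome depends on reading the same-date rule as covering baseline.

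Three further points stand. A compliant site will have a central duplicate of C1D8 and C1D15 glucose, which preserves the post-baseline grade if fully dated, though not the baseline. Random glucose is allowed from C1D8 and may be analysed separately from the fasting screening value, so the example requires both values to be fasting. Core Phase laboratory work is mainly central and missing values are queried (Protocol 7.2.2.5, 9.4), so partial dates are probably uncommon.

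The strongest objection is that the PDS may already contain a better rule. That cannot be checked, and it would not make the printed table correct.

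**Conclusion.** The point holds as a minor error in the printed rule. With only the day missing, a post-dose sample is exposed only if it falls in the calendar month of first dose: about 77% of C1D8, 54% of C1D15 and 8% of C2D1 samples, and none from C2D15 on. With the month also missing, any sample in the start year is exposed.

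These shares assume uniform start dates and are conditional on a date being partial. How often that happens is unknown; on the assumed range, fewer than two patients per cohort would be affected. The consequence is a wrong baseline in shift tables, worst post-baseline grades and change-from-baseline summaries, in either direction. AE tables and listings are not affected, nor is the primary endpoint, since tumour-assessment dates have a separate rule.

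**What to change.** In SAP 5.1.2, and in the PDS to match:

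1. Limit Table 5-1 to adverse-event and concomitant-medication start dates.
2. State that a laboratory, ECG or vital-sign record with an imputed date is never used as baseline when a record with a complete pre-treatment date exists. This is the essential repair.
3. Place a partially dated assessment by its recorded visit where there is one.
4. Where there is no visit label and the record falls in the start month (or the start year, if the month is missing) and cannot be shown to be pre-treatment, count it as on-treatment for the worst post-baseline grade and flag it in the listings. This is needed because urgent local results go on an unscheduled eCRF page (Protocol 7.2.2.5, below Table 7-5) and may carry no visit label.

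If the PDS already does this, only the SAP table needs aligning. The cost is a few sentences and a small programming change. The downside is that a few undatable records drop out of by-visit summaries, and a rare true pre-dose record may be counted as on-treatment.

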5.1.2.1 Other imputations

Incomplete date of initial diagnosis of cancer and date of most recent recurrence

Missing day is defaulted to the 15th of the month and missing month and day is defaulted to 01-Jan.

Incomplete assessment dates for tumor assessment

All investigation dates (e.g. MRI scan, CT scan) must be completed with day, month and year. If one or more assessment dates are incomplete but other investigation dates are available, this/these incomplete date(s) are not considered for calculation of the assessment date and assessment date is calculated as the latest of all investigation dates (e.g. MRI scan, CT scan) if the overall response at that assessment is CR/PR/SD/UNK. Otherwise – if overall response is progression – the assessment date is calculated as the earliest date of all investigation dates at that evaluation number. If all measurement dates have no day recorded, the 1st of the month is used. If the month is not completed, for any of the investigations, the respective assessment will be considered to be at the date which is exactly between previous and following assessment. If a previous and following assessment is not available, this assessment will not be used for any calculation.

Applying the cut-off to tumor assessment

For tumor related assessments, if an evaluation has some assessments done prior to cut-off date and others after the cut-off date, then the evaluation is considered post-cut-off date and will be excluded from analysis.

5.2 AEs coding/grading

Adverse events are coded using the Medical dictionary for regulatory activities (MedDRA) terminology.

AEs will be assessed according to the Common Terminology Criteria for Adverse Events (CTCAE) version 4.03 .

The CTCAE represents a comprehensive grading system for reporting the acute and late effects of cancer treatments. CTCAE grading is by definition a 5-point scale generally corresponding to mild, moderate, severe, life threatening, and death. This grading system inherently places a value on the importance of an event, although there is not necessarily proportionality among grades (a grade 2 is not necessarily twice as bad as a grade 1).

5.3 Laboratory parameters derivations

Grade categorization of lab values will be assigned programmatically as per NCI Common Terminology Criteria for Adverse Events (CTCAE) version 4.03 (specify version used in the RAP). The calculation of CTCAE grades will be based on the observed laboratory values only, clinical assessments will not be taken into account. The criteria to assign CTCAE grades are given in Novartis internal criteria for CTCAE grading of laboratory parameters. The latest available version of the document based on the underlying CTCAE version 4.03 at the time of

analysis will be used. The Novartis internal CTC grading document has been added as appendix 2 to the present document. For laboratory tests where grades are not defined by CTCAE v 4.03, results will be graded by the low/normal/high (or other project-specific ranges, if more suitable) classifications based on laboratory normal ranges.

A severity grade of 0 will be assigned for all non-missing lab values not graded as 1 or higher. Grade 5 will not be used. For laboratory tests that are graded for both low and high values, summaries will be done separately and labelled by direction, e.g., sodium will be summarized as hyponatremia and hypernatremia.

Imputation Rules

CTC grading for blood differentials is based on absolute values. However, this data may not be reported as absolute counts but rather as percentage of WBC.

If laboratory values are provided as ' $<X$ ' (i.e. below limit of detection) or ' $>X$ ', prior to conversion of laboratory values to SI unit, these numeric values are set to X .

The following rules will be applied to derive the WBC differential counts when only percentages are available for a xxx differential

$$\text{xxx count} = (\text{WBC count}) * (\text{xxx \%value} / 100)$$

Further derivation of laboratory parameters might be required for CTCAE grading. For instance, corrected calcium can be derived using the reported total calcium value and albumin at the same assessment using the following formula:

$$\text{Corrected Calcium (mg/dL)} = \text{Calcium (mg/dL)} - 0.8 [\text{Albumin (g/dL)} - 4]$$

In order to apply the above formula, albumin values in g/L will be converted to g/dL by multiplying by 0.1, calcium values in mmol/L will be converted to mg/dL by dividing by 0.2495. For calculation of laboratory CTC grades 0 and 1, the normal range for derived corrected calcium is set to the same limits (in mg/dL) as for calcium.

CTC grades for the derived absolute WBC differential counts (neutrophils, lymphocytes) and corrected calcium will be assigned as described above for grading

